CMAP	Compound Motor Action Potential
CRF	Case report form
CTA	Clinical trial agreement
CTI	Cavotricuspid isthmus
DD	Device deficiency
e.g.	For example,
ECG	Electrocardiogram
EMG	Electromyography
EP	Electrophysiology
FD	Financial disclosure
FAL	Foreseeable adverse event list
FDA	Food and Drug Administration
GCP	Good clinical practice
ID	Identification
IC	Informed consent
IDE	Investigational device exemption
IFU	Instructions For Use
IRB	Institutional review board
ISO	International Organization for Standardization

Term	Definition
ICMJE	International Committee of Medical Journal Editors
LAD	Left atrial diameter
LVEF	Left ventricular ejection fraction
MDD	Medical Device Directive
MEC	Medical ethics committee
MedDRA	Medical Dictionary for Regulatory Activities
MI	Mitral isthmus
NIHSS	National Institute of Health Stroke Scale
NOAC	Novel oral anticoagulant
NYHA	New York Heart Association
N ₂ O	Nitrous Oxide
PAF	Paroxysmal atrial fibrillation
PV	Pulmonary vein
PVI	Pulmonary vein isolation
REB	Research Ethics Board
RF	Radiofrequency
RI	Right inferior
RS	Right superior
SAE	Serious adverse event
SADE	Serious adverse device effect
SAP	Statistical analysis plan
TEE	Transesophageal echocardiogram
TIA	Transient ischemic attack
TTE	Transthoracic echocardiogram
US	United States
UADE	Unanticipated adverse device effect
USADE	Unanticipated serious adverse device effect

2. Synopsis

Title	ArcticLine Feasibility Study ("Study")																	
Clinical Study Type	Feasibility																	
Product Name	ArcticLine Cardiac Cryoablation Catheter ("ArcticLine Catheter")																	
Sponsor	United States Medtronic, Inc. [name] [name]																	
Local Sponsor	Canada Medtronic of Canada [name] Canada [contact]																	
Indication under investigation	The proposed indication for the ArcticLine Catheter evaluated in this Study is as follows: The ArcticLine Cardiac Cryoablation Catheter is indicated for creating endocardial linear lesions, subsequent to successful pulmonary vein isolation, during cardiac ablation procedures for treatment of patients with persistent atrial fibrillation. The ArcticLine Catheter can also be used to treat typical atrial flutter.																	
Investigation Purpose	Collect preliminary safety and effectiveness data on the ArcticLine Catheter																	
Product Status	
  
 Component	Model Number	Geography	
   
 ArcticLine™ Cardiac Cryoablation Catheter	2AL35	Canada (investigational) US (investigational)	
 
 CryoConsole™, including Accessories	106A3, Models 10000-008-04 or 10000-008-08	Canada (commercial) US (commercial)	
 
 ArcticLine™ Catheter File	Not applicable	Canada (investigational) US (investigational)	
 
 FlexCath® Advance Steerable Sheath 12 Fr	4FC12	Canada (investigational) US (investigational)	
  
			Component	Model Number	Geography	ArcticLine™ Cardiac Cryoablation Catheter	2AL35	Canada (investigational) US (investigational)	CryoConsole™, including Accessories	106A3, Models 10000-008-04 or 10000-008-08	Canada (commercial) US (commercial)	ArcticLine™ Catheter File	Not applicable	Canada (investigational) US (investigational)	FlexCath® Advance Steerable Sheath 12 Fr	4FC12	Canada (investigational) US (investigational)
Component	Model Number	Geography																
ArcticLine™ Cardiac Cryoablation Catheter	2AL35	Canada (investigational) US (investigational)																
CryoConsole™, including Accessories	106A3, Models 10000-008-04 or 10000-008-08	Canada (commercial) US (commercial)																
ArcticLine™ Catheter File	Not applicable	Canada (investigational) US (investigational)																
FlexCath® Advance Steerable Sheath 12 Fr	4FC12	Canada (investigational) US (investigational)																

	Component	Model Number	Geography
	Arctic Front Advance® Cardiac Cryoablation Catheter	2AF233	Canada (commercial)
		2AF283	Canada (commercial)
		2AF234	US (investigational)
		2AF284	US (investigational)
	Freezor® MAX Cardiac Cryoablation Catheter	209F3	Canada (commercial)
		209F5	Canada (commercial)
		239F3	US (investigational)
		239F5	US (investigational)
Primary Objective(s)	Estimate the incidence of ArcticLine Catheter-related and ArcticLine cryoablation procedure-related serious adverse events (SAEs) with an onset date within 7 days post-procedure		
Ancillary Objective(s)	
There are seven (7) ancillary objectives for the study, as follows:
 
 1. Estimate the percentage of patients with acute treatment success of the ArcticLine Catheter at the left atrial roof and posterior wall in patients with demonstrated entrance block of all pulmonary veins and who underwent roof and posteriorwall ablation with ArcticLine. 2. Estimate the percentage of patients with acute treatment success of the ArcticLine Catheter at the mitral isthmus in patients who underwent mitral isthmus ablation withArcticLine. 3. Estimate the percentage of patients with acute treatment success of the ArcticLine Catheter at the CTI in patients who underwent CTI ablation with ArcticLine. 4. Characterize chronic treatment success of the ArcticLine Catheter in patients with demonstrated entrance block of all pulmonary veins. 5. Estimate the incidence of ArcticLine Catheter-related and ArcticLine cryoablation procedure-related serious adverse events (SAE) through the 6 month visit. 6. Characterize procedural data (e.g. procedure time, fluoroscopy time, fluoroscopy dose, number of applications, left atrial dwelltime) 7. Estimate the incidence of adverse events through the 6 month visit that meet the following, as defined in the Clinical Investigation Plan: 
 • Atrioesophageal fistula • Cardiac perforation/tamponade • Cerebrovascular accident • Coronary artery spasm • Death • Esophageal injury • Lung injury (includinghemoptysis) • Major bleeding • Myocardial infarction • Pericarditis 		

	
 • Phrenic nerve injury (ongoing from hospital discharge) • Pulmonary vein stenosis • Symptomatic persistent iatrogenic atrial septal defect • Transient ischemic attack • Vagal nerve injury • Vascular access complications
Study Design	
The study is a prospective, interventional, multi-center, non-randomized, single arm, unblinded clinical study. Adult subjects with history of persistent atrial fibrillation (AF), including those with concomitant typical atrial flutter (AFL), to undergo ablation of:
 
 • Pulmonary veins (required, unless prior successful pulmonary vein isolation confirmed at start of study procedure), • Left atrial roof and posterior wall (required) • Mitral isthmus (optional, as determined by investigator), and • Cavo-tricuspid isthmus (required if subject has a history of AFL or AFL is induced during the study procedure, otherwise optional as determined by investigator). 
Study subjects from all participating geographies will be followed for 6 months after the index ArcticLine procedure and will be exited from the study at the conclusion of the 6 month follow-up visit.
 
Note: Safety and effectiveness data collected beyond the 6 month visit due to CIP Version 4 follow-up requirements will be adjudicated and included in the final report.

Sample Size	Up to 15 subjects will be treated with the ArcticLine Catheter
Inclusion/Exclusion Criteria	
Inclusion Criteria
 
 • Documentation of symptomatic persistent AF: 
 ○ Defined as having a continuous episode that is sustained beyond 7 days documented via consecutive ECG recordings, or ○ Defined as having a continuous episode that is sustained beyond 7 days documented by an ECG recording and one doctor note indicating the patient had symptoms consistent with AF • Age 18 through 80 years old • Failure or intolerance of at least one Class I or III antiarrhythmic drug • Subject is able and willing to consent to participate in the study and will commit to completion of all follow-up requirements 
Exclusion Criteria
 
 • Longstanding persistent AF, defined as continuous AF greater than 12 month duration • Left atrial diameter greater than 5.0 cm • Active systemic infection • History of thromboembolic event within the past 6 months or evidence of intracardiac thrombus at the time of the procedure

- Prior left atrial ablation attempt, with exception of:
 - Any pulmonary vein isolation attempt to treat AF, or
 - Successful ablation to treat Wolff-Parkinson White syndrome
- History of left atrial tachycardia
- History of cardiac ablation within 90 days of planned clinical study procedure
- Planned concomitant ventricular ablation¹
- Cryoglobulinemia
- Structural heart disease of clinical significance including:
 - NYHA Class IV Heart Failure
 - Diagnosed with NYHA Class III Heart Failure for more than six months at time of the study ablation procedure
 - LVEF less than 35%
 - Any cardiac surgery (e.g. CABG) within 3 months of the ablation procedure
 - Any mechanical heart valve, prior aortic or tricuspid valve replacement (e.g. valvotomy, valve replacement) or tricuspid valve repair
 - Severe mitral valve regurgitation or stenosis
 - Significant congenital anomaly or anatomy unable to accommodate device
- Prior surgical maze procedure
- Unstable angina
- Myocardial infarction within 3 months of the ablation procedure
- Presence of primum or secundum atrial septal defect
- Anomalous pulmonary venous return
- Prior surgery for congenital heart disease including atrial septal defect repair
- Hypertrophic cardiomyopathy with LV septal wall thickness >1.5 cm
- Uncontrolled hyperthyroidism
- Thrombocytosis, thrombocytopenia (including history of heparin-induced thrombocytopenia)
- Severe comorbidity or poor general physical/mental health that, in the opinion of the investigator, will not allow the subject to be a good study candidate
- History of blood clotting or bleeding abnormalities
- Contraindication to all anticoagulation (e.g. novel oral anticoagulants, heparin or warfarin)
- Pregnant, nursing or planning to become pregnant during study duration

¹ Concomitant ventricular ablation will be allowed in the proposed feasibility clinical study if determined to be in the best interest of the subject at the time of the procedure as assessed by the Investigator. However, the ArcticLine Catheter may not be used for these purposes.

- Enrollment in another clinical trial without prior approval from Medtronic
- Presence or use of left atrial appendage closure device
- Presence of or planned implantation of a pacemaker, implantable cardiac defibrillator, implantable loop recorder or cardiac resynchronization device with permanent lead placement
- Pre-existing hemidiaphragmatic paralysis
- Life expectancy less than one year
- Known drug or alcohol dependency
- Existing pulmonary vein stent(s)

Study Procedures and Assessments	Baseline	Procedure	Discharge	1 week ¹	3 month ²	6 month ²	Unscheduled	Repeat Ablation
	Informed Consent	X						
Inclusion/Exclusion Criteria	X							
Medical History	X							
Physical Exam	X							
AAD & Anticoagulation Medication Review	X		X	X	X	X	X	
Pregnancy Screen ³	X							
Arrhythmia Symptom Review	X			X	X	X	X	
NIHSS Assessment	X		X					X ⁶
Transthoracic Echocardiogram (TTE) ⁴	X							
Transesophageal Echocardiogram (TEE)	X							
12 Lead ECG	X		X		X	X	X	
Procedure Information		X						X
Post-ablation endoscopy ⁵		X						X
24 Hr Continuous Monitoring with Holter						X		

	Baseline	Procedure	Discharge	1 week ¹	3 month ²	6 month ²	Unscheduled	Repeat Ablation
Patient Activated Ambulatory ECG Monitor					Monthly and symptomatic episodes			
Adverse Events	As they occur							
Device Deficiencies	As they occur							
Study Deviations	As they occur							

Notes:
 
¹Phone visit and/or office visit with Nurse Coordinator
 
²Multiple modes of data collections may be employed to support the collection of required visit data at the 3 and 6 month visits such as: In office patient clinic visit, direct to patient contact (i.e. telephone, email, mail contact, etc.), and remote technology transmissions/uploads.
 
³Female subjects of child bearing potential only
 
⁴Only required if data not available from within 6 months prior to consent date
 
⁵Post-ablation endoscopy is required post-ablation, prior to discharge, only if the subject's esophageal temperature drops below 15 degrees C at any time during the study procedure.
 
⁶For repeat ablations using ArcticLine Catheter, NIHSS will be completed at baseline and discharge.
								
Safety Assessments	
Clinical Events Committee:
 
An independent committee comprised of electrophysiologists not participating in the study will review and adjudicate all adverse events as well as all deaths for subjects participating in the study.
							
Statistics	
No formal hypotheses for this study:
 
 • Data will be reported as collected and no imputation will be performed for missing or incomplete observations. • Analyses are planned at the following time points: 
 ○ After completion of the 15 subject index procedures and 1 week follow-up visit ○ After all subjects have completed follow-up visits through at least the 6 month follow-up visit and have been exited from the study 							

3. Introduction

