6.2. ArcticLine Cryoablation Catheter

The ArcticLine Catheter is a sterile, single use, minimally invasive intravascular catheter specifically designed for cardiac tissue cryoablation via a linear ablation segment. The ArcticLine Catheter is used together with the CryoConsole and related devices. The Catheter is percutaneously advanced to the applicable heart chamber from the femoral access via a transeptal sheath in the vasculature. The effective length is 107 ± 2.0 cm. Once the catheter reaches the applicable atrium, it is positioned and the ablation segment creates a linear lesion at the targeted location. The ArcticLine Catheter is not approved for sale in any geography.

The proposed indication for the ArcticLine Catheter evaluated in this Study is as follows:

The ArcticLine Cardiac Cryoablation Catheter is indicated for creating endocardial linear lesions, subsequent to successful pulmonary vein isolation, during cardiac ablation procedures for treatment of patients with persistent atrial fibrillation. The ArcticLine Catheter can also be used to treat typical atrial flutter.

Note: Patients enrolled in the study must have persistent atrial fibrillation. For those subjects who also have concomitant typical atrial flutter or the investigator determines a prophylactic CTI line is warranted, the ArcticLine Catheter will be used to create a CTI line for treatment. Patients with stand-alone typical atrial flutter will not be enrolled in the study.

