8.4. Procedure

The Investigator is to perform the procedure according to the procedural steps in this CIP and the applicable Instructions for Use for all devices (except for investigational uses as described in this CIP). Current recommendations for anticoagulation are found in the 2017 HRS/EHRA/ECAS/APHS/SOLAECE Expert Consensus Statement on Catheter and Surgical Ablation of Atrial Fibrillation² and 2014 Focused Update on the Canadian Cardiovascular Society Guidelines for the Management of Atrial Fibrillation.¹⁷

8.4.1. High Level Procedure Overview:

Appropriate sedation and venous access should be attained per the Investigator's standard practice according to their institution's pre-established procedures/guidelines at the time of the procedure. Investigator may choose compatible guidewires and mapping catheters at their discretion. The FlexCath Advance 12Fr sheath must be used for the deployment of the Arctic Front Advance and ArcticLine ablation catheters. Deploy diagnostic catheters and perform transseptal puncture.

Perform a baseline voltage map of the left atrium using a 3D mapping system (e.g. NavX, Rhythmia). Recommended settings for minimum voltage in this study is 0.2mV.

Perform baseline mapping of the pulmonary veins to assess for pulmonary vein potentials using a circular mapping catheter (e.g. Achieve Advance) to determine if PVI is required. If yes, perform the pulmonary vein isolation procedure using Arctic Front Advance Catheter as per Section 8.4.5.

If PVI ablation is performed, repeat voltage mapping of the left atrium using a 3D mapping system.

If the investigator determines the subject should move forward with ArcticLine ablation, perform the following required linear ablations using the ArcticLine Catheter as per Section 8.4.6:

- Left atrial roof line
- Left atrial posterior wall line

Note: An example where the investigator may choose not to move forward with ArcticLine ablation and instead, exit the subject from the study, is when a subject has previously undergone PVI and has minimal pulmonary vein reconnection which, in the opinion of the investigator, only requires touch-up ablation.

¹⁷ Verma A, et al. 2014 Focused Update of the Canadian Cardiovascular Society Guidelines for the Management of Atrial Fibrillation. *Canadian Journal of Cardiology*. 30 (2014) 1114-1130.

At the investigator's discretion, perform optional linear ablations at the following anatomic targets using the ArcticLine Catheter:

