- Mitral isthmus (see Section 8.4.7)
- CTI (see Section 8.4.8)

At the investigator's discretion, use pacing maneuvers to determine the immediate effect of the ArcticLine ablation(s). Note: Direct Current (DCCV) or pharmacological cardioversion may be considered at any point during the procedure when restoration of sinus rhythm (SR) will assist in assessing the effectiveness of cryoablations or deemed necessary for the benefit of the patient.

Repeat ArcticLine ablation(s), as necessary to achieve conduction block, as described in Sections 8.4.6-8.4.8.

Upon completion of a minimum 30-minute wait time from the last ArcticLine ablation for each respective anatomy target, perform repeat voltage map of the left atrium using a 3D mapping system with the recommended settings. Use of 3-D mapping following the 30-minute waiting period should be performed while the subject is in Sinus Rhythm.

Notes:

- Reference ArcticLine Technical Guidance for recommendations on pacing maneuvers and 3D mapping settings.
- If Investigator is unable to successfully complete a lesion with the ArcticLine Catheter after a minimum of four (4) ArcticLine ablation applications, they may cross over to another FDA approved catheter. This will be considered an ArcticLine treatment failure.
- Temperatures of -80°C are expected with use of the ArcticLine Catheter.
- The ArcticLine Catheter ablation segment should be completely outside of the sheath prior to initiating an ablation. Freezing in the sheath may result in occluding the saline drip.
- Methods used to assess for conduction block must be documented and reported.
- Copies of voltage maps from ArcticLine procedures are to be sent to Medtronic.

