8.4.8. Linear Cryoablation with ArcticLine Catheter: Cavotricuspid Isthmus

If the investigator chooses to perform a CTI line ablation, perform the following steps:

Advance the ArcticLine Catheter to the CTI by positioning between the inferior vena cava and tricuspid annulus. Phrenic nerve monitoring must be done in accordance with Table 4.

Assess the positioning and contact via fluoroscopy, ultrasound imaging, or other technique. Reposition as needed.

Perform the cryoablation. Cryoapplications of four (4) minutes is recommended at the CTI.

- Note: It is the investigator's discretion to assess necessity of additional freezes to complete the desired ablation line.

Assess the CTI line for bi-directional conduction block using pacing maneuvers and/or 3D mapping following a 30-minute wait.

Notes:

- The ArcticLine Catheter ablation segment should be completely outside of the sheath prior to initiating the ablation. Freezing in the sheath may result in occluding the saline drip.
- Upon the Investigator's assessment of procedure completion, Isoproterenol and/or adenosine may be used.
- Use of another catheter, other than the ArcticLine Catheter, for gap completion of the cavotricuspid isthmus line will be considered a treatment failure.

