All subjects with index ArcticLine cryoablation procedures where the CTI line was attempted will be included in this metric.

7.26 Ancillary Objective 4

Characterize chronic treatment success of the ArcticLine Catheter in patients with demonstrated entrance block of all pulmonary veins.

Ancillary Endpoint #4

Chronic treatment success is the opposite of chronic treatment failure. Treatment failure is any of the following:

- AF/AFL/AT episodes of at least 30 seconds duration from the end of the 90 day blanking period through the 6 month visit.
- Per section 8.6.1 of the CIP, the initiation of a new Class I or III Antiarrhythmic Drug (AAD) after the 90 day blanking period, or a dose increase in a previously failed Class I or III AAD after the 90-day blanking period
- Reablation for the treatment of recurrent AF/AT/AFL after the 90 day blanking period

Note: For subjects who did not receive CTI ablation with ArcticLine Catheter, documented occurrence and treatment of typical right-sided cavotricuspid isthmus dependent atrial flutter during follow-up will not contribute to this endpoint. Subjects who (A) have “NOT APPLICABLE, CTI ABLATION NOT PERFORMED” indicated on all Procedure CRF’s, and (B) only have arrhythmia occurrences that the core lab determines to be typical CTI-dependent atrial flutter (as indicated in the recurrence type field on the core lab CRF; see below) will not be considered as chronic treatment failures on grounds of AFL recurrence. They may still experience chronic treatment failure for AF or AT, atypical atrial flutter, medication failures or repeat ablations outside of the blanking period.

Does the Assessment Indicate Recurrence of AF/ AFL/ AT	If Yes, Recurrence Type
LOV (2)	 ATRIAL FIBRILLATION  ATRIAL FLUTTER, CTI-DEPENDENT  ATRIAL FLUTTER, OTHER TYPE  ATRIAL TACHYCARDIA

Medication failures will be determined by calculating the pre-ablation maximum ongoing dose for each generic drug name (using TMS classification) for each patient. All medications described as “ongoing”

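### The protocol both requires a CTI line in subjects with typical flutter and leaves it to the investigator, so an omitted line has no defined deviation status and Objective 4's flutter exemption extends to subjects for whom the synopsis required the line

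*Protocol*

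**What the plan says.** Four places in the current protocol set the rule for the CTI line.

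- Synopsis, Study Design: "required if subject has a history of AFL or AFL is induced during the study procedure, otherwise optional as determined by investigator".
- Section 6.2 uses mandatory wording: "the ArcticLine Catheter will be used to create a CTI line for treatment". This covers concomitant typical flutter and the prophylactic case. It does not mention flutter induced during the procedure.
- Section 8.4.1: "At the investigator's discretion, perform optional linear ablations at the following anatomic targets using the ArcticLine Catheter". The list that follows includes "CTI (see Section 8.4.8)".
- Section 8.4.8 opens: "If the investigator chooses to perform a CTI line ablation".

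Neither part of section 8.4 makes an exception for a subject with known or induced flutter.

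Three analysis rules depend on what was done at the CTI.

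- Objective 3 (protocol 12.4, SAP 7.25) counts only index procedures in which a CTI line was attempted.
- Objective 4 (protocol 12.5, SAP 7.26) has an exemption for subjects without ArcticLine CTI ablation: "documented occurrence and treatment of typical right-sided cavotricuspid isthmus dependent atrial flutter during follow-up will not contribute to this endpoint". The SAP applies it when every Procedure CRF marks CTI ablation as not performed and the core lab finds only CTI-dependent flutter. Neither document refers to flutter history or inducibility here.
- SAP 7.26 adds confirmed CTI block, where applicable, to the criteria for entering the Objective 4 set. The list in protocol 12.5 does not contain this criterion.

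**The concern.** Protocol 8.11 defines a deviation as something that did not happen according to the plan, and SAP 7.1.2 tabulates and lists deviations. Omitting the CTI line in a subject with known typical flutter departs from the synopsis and section 6.2 but complies with sections 8.4.1 and 8.4.8. Two people applying the documents correctly could produce different deviation counts.

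The second consequence is for Objective 4. Exempting typical flutter is reasonable where the CTI line was optional and was not made, because the device was not used at that target. As written, the exemption also covers subjects for whom the synopsis called for the line. In those subjects a typical-flutter recurrence would leave no trace in the chronic success estimate. Treating typical flutter is part of the study purpose (section 3.2) and of the proposed indication (section 6.2), and the results are meant to inform a pivotal study.

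**Working it through.** **The plan's own precision figure.** SAP section 6 gives a width of 32% for the exact 95% interval at 1 event in 15 procedures. Clopper-Pearson gives 0.17% to 31.95%, a width of 31.8 points, which rounds to 32%. The figure is not in dispute. It confirms the exact method, which Objective 3 also uses.

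**One subject under the two readings.** Take a treated subject with known typical flutter and no CTI line.

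| Question | Synopsis and 6.2 | 8.4.1 and 8.4.8 |
|---|---|---|
| Is the omission a deviation? | Yes | No |
| In the Objective 3 denominator? | No, because no line was attempted | No |
| In the Objective 4 set, if the other acute criteria are met? | Yes | Yes |
| Does later CTI-dependent flutter count as failure? | No | No |

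The last two rows agree because the exemption ignores which rule applied. SAP 7.1.2 does not exclude the subject either, since an omitted CTI line is not among its exclusion conditions.

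**Objective 4 by CTI status, under SAP 7.26.**

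- Ablated with block confirmed: in the set, and typical flutter counts.
- Ablated without confirmed block: out of the set.
- Not ablated: in the set, and typical flutter is exempt.

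**Size.** Let n be the size of the Objective 4 set, f the failures from other causes, and k the subjects with known or induced flutter, no ArcticLine CTI line, and CTI-dependent flutter as their only failure. With no censoring the Kaplan-Meier estimate is a simple proportion:

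- Main definition: (n − f)/n
- Counting typical flutter in those k subjects: (n − f − k)/n
- Difference: k/n

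The documents give 15 treated subjects. They do not give n, f or k, so the values below are assumptions.

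- n = 15, k = 1: 1/15 = 6.7 points.
- n = 15, f = 3, k = 1: 12/15 = 80.0% against 11/15 = 73.3%.
- n = 15, f = 3, k = 2: 12/15 = 80.0% against 10/15 = 66.7%.
- n = 10, k = 1: 1/10 = 10 points. The acute-block criteria can make the set smaller than 15.
- k = 0: no difference.

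**Objective 3.** The number of attempted CTI lines sets the precision. With one failure (denominators assumed), the exact 95% interval is 28.4% to 99.5% at n = 5 (71 points wide), 55.5% to 99.7% at n = 10 (44 points) and 68.1% to 99.8% at n = 15 (32 points). This says nothing about the direction of any bias.

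**The case against.** The strongest reply has four parts.

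- **The exemption is deliberate and narrow.** It is pre-specified in both documents and concerns a target where the device was not used. AF, AT, atypical flutter, medication failures and repeat ablations outside blanking can still be failures. This stands as a defence of the main definition, which should stay. It does not explain why the exemption should extend, without being reported, to subjects for whom the synopsis required the line.
- **Objective 3 is unaffected in principle.** A reader might infer that operator choice inflates CTI success. The documents do not support that. The objective is defined in patients who underwent CTI ablation, and the line is optional for subjects without flutter even under the synopsis. Omitting it removes a possible success as well as a possible failure. What remains is a reporting point: how many subjects with flutter had no attempt.
- **Rewording comes too late for conduct.** The note in SAP 7.2.2 says that all procedures are complete. This stands. Reconciliation can now affect only deviation classification and reporting.
- **Some reporting already exists.** SAP 7.1.2 lists deviations, and the interim report in SAP 7.6 lists procedures and their anatomical targets. Neither sets CTI status against flutter history, so a small gap remains.

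These are also descriptive ancillary objectives with no hypothesis test, and the primary safety endpoint does not depend on CTI status.

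**Conclusion.** The contradiction is real and is in current text. The synopsis (known or induced flutter) and section 6.2 (concomitant typical flutter) cannot both be followed alongside sections 8.4.1 and 8.4.8 when the investigator declines the line. Deviation status is undefined for such a subject, and the Objective 4 exemption covers that subject without any disclosure.

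The numerical effect is conditional. It is 6.7 points per affected subject if all 15 are in the Objective 4 set with no censoring, and more if the set is smaller. Censoring would alter the step. It is zero if no subject with flutter went without the line, or if none of those had typical flutter as the only failure. The documents do not say how many such subjects exist.

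A reader might go further and infer that chronic success was raised by leaving subjects with flutter untreated at the CTI. Nothing in the documents shows that this happened or was intended. Nor would reconciliation remove all discretion: the line would stay optional for subjects without flutter even under the synopsis rule, and the exemption would still properly apply to them.

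The point is worth correcting because it is cheap, but it does not threaten the primary objective.

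**What to change.** 1. **Protocol.** Reconcile the synopsis and section 6.2 with sections 8.4.1 and 8.4.8, and state whether induced flutter falls under the section 6.2 wording. No view is offered on which clinical rule is right.
2. **SAP 7.1.2.** List every treated subject with known or induced typical flutter and no ArcticLine CTI line, and classify each against the reconciled text. Report the count beside the Objective 3 result.
3. **SAP 7.26.** Keep the main Objective 4 definition. Add one sensitivity estimate, by the same Kaplan-Meier method, that counts typical-flutter recurrence as failure in the listed subjects.
4. **Data source.** The CRF excerpts in the SAP show CTI status and the core lab's recurrence type, and protocol 8.3 collects medical history at baseline. No excerpt shows a field for induced flutter. The full CRFs are under separate cover, so the sponsor should confirm where induced flutter is recorded.

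The cost is a wording change, one listing and one extra row. SAP 7.8 already allows a further SAP version or an explanation in the final report. If induced flutter was not captured on a CRF, it would have to be retrieved from procedure records for at most 15 subjects.
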